## 2 Study Objectives

Primary Objective: The primary objective is to examine changes in ratings of ADHD symptoms and SCT. The primary measure of ADHD symptoms will be the total score on the ADHD Rating Scale (ADHD-RS) with prompts [16]. The primary measure of SCT will be the Barkley SCT Scale.

Secondary Objectives:

- 1) Examine changes in the BRIEF-A Metacognition Index and Motivation Subscales as these subscales are more closely related to measures of arousal and motivation than other subscales of the BRIEF-A.
- 2) Examine changes in ratings of functional impairment via the B Barkley Functional Impairment Scale (BFIS).
- 3) Examine changes in a battery of neuropsychological tests of arousal and alerting, including:
  - i. The Cambridge Neuropsychological Testing Automated Battery (CANTAB) ADHD battery: A validated battery of 4 tests which assess motor speed (Motor Control Task), spatial working memory (Spatial Working Memory), response inhibition (Stop Signal Task), and sustained attention (Rapid Visual Information Processing) [17]. In addition, we have included the Attention Switching Task (AST), an useful test in defining the cognitive phenotype in individuals with ADHD + high IQ. Measures of reaction time and reaction time variability will be

CONFIDENTIAL

examined.

- ii. The Wechsler Adult Intelligence Scale-IV (WAIS-IV): Coding and Symbol Search subtests will be used to evaluate processing speed [18].
- 4) Examine potential differences in nature and severity of ADHD symptoms (total, inattentive, and hyperactive-impulsive), symptoms of executive function (BRIEF GEC, metacognition, behavioral regulation scales and subscales: Inhibit, Shift, Emotional Control, Initiate, Working Memory, Plan/Organize, Organization of Materials, Monitor), neuropsychological test performance on the CANTAB and WAIS subtests listed above, and impairment ( Barkley Functional Impairment Scale (BFIS)) [27]
- 5) The On-Top scale will be used on treatment outcome in adult ADHD to measure executive functions in daily life.[29][30]

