### 3 Study Design

#### 3.1 General Design

- 1) Total number of subjects/Total sample size: Approximately 120 patients with ADHD (with the final number of subjects depending on the proportion of ADHD subjects who have SCT; we have based our projections on an estimated 50% prevalence) in the phenotype phase (screening visit); 50 adults with ADHD and SCT+ will enter the treatment phase with LDX and placebo. We will analyze data from all subjects who take at least one dose of medication in both blocks. Using a 20% drop-out rate to occur throughout the trial, we estimate that approximately 50 subjects will enroll in the trial; 46 patients will complete the first phase of treatment, 44 patients will complete the intervening placebo washout, and 40 patients will complete each treatment phase.
- 2) Justification for sample size: We will enroll a sufficient number of subjects to recruit 80 patients with ADHD and SCT to enter the treatment study. The 50% prevalence of SCT in adult ADHD has been established in community samples [1, 2]. Power for this study was calculated using PASS [22] based on the primary outcome, i.e. change between baseline and week 4 of treatment on the Barkley SCT scale. Previous studies suggest that the upper bound of the effect size for the comparison of ADHD

CONFIDENTIAL

medications vs. placebo for ADHD symptoms varies between 1.2 and 1.5 standard deviations. Using a conservative estimate of effect that is half as robust for SCT as ADHD we based on our calculations on a 0.6 ES for SCT symptoms. The primary comparison will be a reduction in SCT symptoms on LDX vs. placebo. With 45 evaluable patients with SCT we will have 80% power to detect an effect size (ES) of 0.6 using a two-sided test with a type I error of 0.05.

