### **3.3 Secondary Study Endpoints**

The secondary study endpoints are to define the SCT phenotype and determine similarities and differences between adults with ADHD with and without SCT on SCT symptoms, executive function symptoms, nature and severity of ADHD symptoms, and neuropsychological profile

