## **6 Study Procedures:**

CONFIDENTIAL

This material is the property of the NYU School of Medicine and Langone Medical Center. Do not disclose or use except as authorized in writing by the study sponsor

	Visit 1	Visit 2	Visit 3	Visit 4	Visit 5	Visit 6	Visit 7	Visit 8	Visit9	Visit 10	Visit 11
Study Procedures and Assessments	Week -3-0	Week 0	Week 1	Week 2	Week 3	Week 4	Week 6	Week 7	Week 8	Week 9	Week 10
	Screening	Baseline 1	Treatment (LDX or PBO) 1			EOT 1	End of PBO Washout/ Baseline2	Treatment (LDX or PBO) 2			EOT 2
SCREENING											
Consent	X										
Demographics	X										
M.I.N.I	X										
ACDS v1.2	X										
Medical History	X										
Psychiatric History	X										
Medical Review of Systems	X										
Physical Exam	X										
Hematology, Chemistry, Urinalysis, and UDS	X										
Urine Pregnancy Test	X										
ECG	X										
Review Eligibility	X	X	X								
EFFICACY											
ADHD-RS		X		X	X	X	X	X	X	X	X
Barkley SCT Scale		X		X	X	X	X	X	X	X	X
CGI-S		x		X	X	X	X	X	X	X	X
SAFETY											
Vital Signs		X	X	X	X	X	X	X	X	X	X
C-SSRS		X	X				X	X			X
Concomitant Medications		X	X	X	X	X	X	X	X	X	X
Adverse Events		X	X	X	X	X	X	X	X	X	X
NEUROPSYCHOLOGICAL BATTERY/EXECUTIVE FUNCTIONING											
CANTAB ADHD		x					X	X			X
WAIS-CODING & SYMBOL SEARCH		X					X	X			X
BRIEF-A		X					X	X			X
BFIS		X					X	X			X
ON-TOP		X									
OTHER											
Dose Dispense/ Adjustment			X	X	X	X			X	X	X
Drug Accountability				X	X	X	X	X	X	X	X

CONFIDENTIAL

This material is the property of the NYU School of Medicine and Langone Medical Center. Do not disclose or use except as authorized in writing by the study sponsor

**STUDY VISIT SCHEDULE:** This is a two part study. Patients will sign this consent form and be asked to do the following: Visit the study doctor weekly over a 12-week period, communicate over the phone between visits 6 and 7 and approximately 1 week after visit 10, and follow study instructions. In addition, patients who participate in the second part of the study will be asked to take study drug as instructed at the same time each day. Patient will have their blood drawn once in the study about 10mls will be collected for hematology and blood chemistry.

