### **6.2 Visit 2 (Baseline 1) Day 0**

Baseline visit: During this visit subjects will have all tests/procedures completed and reviewed. We will review medical history, any current of adverse events (AE) and concomitant medications (CM) since screening visit. We will perform vital signs and C-SSRS. We will ensure completion of any assessments not finished during the screening visit. Subjects will be given medication to take the next morning if they are found to have both ADHD and SCT. Study Medication is not dispensed until all assessments and procedure are complete for the baseline visit

Note: If at the end of this baseline visit, the patient is found to have both ADHD and SCT; they will be invited to continue to the second part of the study. If the patient has both ADHD and SCT, he/she will be given Study Medication (Vyvanse or placebo) to take the next morning. Placebo looks just like Vyvanse but has no active ingredients, like a sugar pill. The study medication can be taken with or without food at the same time every day.

CONFIDENTIAL

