## 7.2 Statistical Methods

Phenotype Phase: Comparisons between the adult ADHD patients cohorts with SCT and without SCT in terms of ADHD symptoms (total, inattentive and hyperactive-impulsive, symptoms of executive function (BRIEF GEC, metacognition, behavioral regulation scales and subscales: Inhibit, Shift, Emotional Control, Initiate, Working Memory, Plan/Organize, Organization of Materials, Monitor), neuropsychological tests (CANTAB ADHD module, WAIS Coding and Symbol Search and Attention Network Test (ANT), and impairment (on Barkley Functional Impairment Scale (BFIS)) will be examine via One Way ANOVA .

Treatment Phase: Changes in outcome ratings in the patients in the treatment phase with LDX and placebo will be modeled with longitudinal generalized estimating equation (GEE) mixed regression models using STATA 12.0 [StataCorp, 2011 #25856] within the framework of the general linear model (GLM). The GLM allows us flexibility in modeling the outcome variable by choosing the appropriate distribution and link function. Each model will predict outcome scores from treatment group (drug vs. placebo), study visit (ordinal predictor), order (drug or placebo first) and the two and three-way interactions among: treatment group, visit, and order. We will first test for order effects and drop effects that are not significant at  $p < .05$ . The visit by treatment interaction indicates if the reduction in symptoms over time significantly differs between drug and placebo. Our primary analyses will be intention

CONFIDENTIAL

[SHIRE SCT s13-01288]  
Version: 03/03/2016

to treat (ITT) but we will explore the data with less conservative per protocol analyses to assure that we do not miss any signals in the data. Because this is a randomized trial, which follows subjects over a short period of time, missing data is not expected to impact our analyses. Should this become an issue, we will impute data using STATA's impute procedure. Using logistic regression, a responder analysis will be conducted using pre-hoc priori criteria for treatment response (30% decreases in total ADHD-RS and Barkley SCT scores). These will be last observation carried forward (LOCF) endpoint models that predict responder status (yes/no) from drug group, order and the drug by order interaction. Baseline symptom scores will be included as covariates.

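### ON-TOP is named as a treatment outcome but is scheduled only once, before the first dose, so Secondary Objective 5 cannot be answered as planned

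*Combined protocol and SAP*

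**What the plan says.** Section 2, Secondary Objective 5, states: "The On-Top scale will be used on treatment outcome in adult ADHD to measure executive functions in daily life". It stands apart from Objective 3, which covers neuropsychological testing ("Examine changes in a battery of neuropsychological tests of arousal and alerting") and describes that battery through CANTAB, with the Attention Switching Task, and two WAIS-IV subtests.

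The schedule table in Section 6 lists ON-TOP last in the block headed "NEUROPSYCHOLOGICAL BATTERY/EXECUTIVE FUNCTIONING", below CANTAB, WAIS, BRIEF-A and BFIS. Its row holds one mark, in the Visit 2 (Week 0, Baseline 1) column.

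Section 6.2 says of that visit: "Study Medication is not dispensed until all assessments and procedure are complete for the baseline visit". The first dose is taken the next morning.

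Sections 6.4, 6.6 and 6.8 (Visits 6, 7 and 11) each call for BRIEF-A, BFIS and the neuropsychological battery. They do not mention ON-TOP.

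Section 3.3 frames the secondary endpoints as a phenotype comparison: "The secondary study endpoints are to define the SCT phenotype and determine similarities and differences between adults with ADHD with and without SCT". Section 7.2 gives a general treatment-phase model: "Changes in outcome ratings in the patients in the treatment phase with LDX and placebo will be modeled with longitudinal generalized estimating equation". Neither section names ON-TOP. Outside Section 2 and the table, the scale appears only in the abbreviation list and the references.

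**The concern.** A treatment outcome in a crossover trial needs at least one value on each treatment. If ON-TOP is measured only before the first dose, it can describe the patients at entry but cannot show what LDX does relative to placebo. The phenotype comparisons in Objective 4 and Section 7.2 do not list it either, so even the Visit 2 value has no named analysis.

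One whole secondary objective is at stake: executive function in daily life as measured by this scale. The imputation fallback in Section 7.2 could not repair the gap, because no patient would have an on-treatment ON-TOP value from which to impute.

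**Working it through.** **Step 1: where each measure is scheduled.** The marks in the Section 6 table were counted against its 11 visit columns and set beside Sections 6.1 to 6.8.

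| Measure | Table | Named in visit text |
|---|---|---|
| ON-TOP | 2 | none |
| BRIEF-A, BFIS | 2, 7, 8, 11 | 6, 7, 11 |
| CANTAB, WAIS (the battery) | 2, 7, 8, 11 | 1, 6, 7, 11 |
| ADHD-RS, Barkley SCT Scale | 2, 4–11 | 3–11 |

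Section 6.2 also allows screening work to be finished at Visit 2: "We will ensure completion of any assessments not finished during the screening visit".

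**Step 2: which visits are on treatment.** Visit 2 precedes the first dose. Visits 3 to 6 fall in block 1, Visit 7 closes the placebo washout, and Visits 8 to 11 fall in block 2. ON-TOP therefore has 1 scheduled value, 0 of them in block 1 and 0 in block 2.

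**Step 3: what the analysis needs.** Section 7.2 reads the treatment effect from the visit-by-treatment interaction. That requires repeated values under both drug and placebo. A single pre-dose value gives neither a change score nor a contrast.

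**Step 4: the size of the gap.** Section 3.1 expects that "46 patients will complete the first phase of treatment", that 44 will complete the washout and that 40 will complete each treatment phase, which is read here as completing both blocks.

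- End-of-block values possible: 46 (Visit 6) + 40 (Visit 11) = 86. ON-TOP scheduled: 0.
- Within-patient LDX–placebo pairs possible: 40. ON-TOP scheduled: 0.
- By the visit text, BRIEF-A and BFIS would each give all 86 values and 40 pairs.

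**Step 5: could a shifted mark change this?** The BRIEF-A and BFIS rows differ from the visit text, so some marks may have moved when the PDF was converted to text. One column to the left of ON-TOP's mark is Visit 1, also pre-dose. One column to the right is Visit 3, which covers block 1 only. A single mark in any column cannot supply both treatments.

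**The case against.** The best counter-reading is that ON-TOP belongs to the neuropsychological battery required at Visits 6, 7 and 11, since the table heading covers both. Objective 3 does not give a closed list, and Section 7.2 adds an attention test that Objective 3 omits. But BRIEF-A and BFIS sit under the same heading and are still named separately from the battery in Sections 6.4, 6.6 and 6.8, so the battery is not the whole block. ON-TOP has its own objective, and its row carries one mark where the four rows above it carry four each. At most the visit text is ambiguous, and a site reading the table would not give the scale on treatment.

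A second objection is that the table may be unreliable as read. If marks were lost altogether, the zero counts would not follow from the table alone. The running text of the visit sections would still omit the scale.

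Three further points stand, but they do not change the result:

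- **Comparator.** The figures of 86 and 40 for BRIEF-A and BFIS come from the visit text. By the table those scales have no Visit 6 mark, which leaves 40 of 86 end-of-block values and no end-of-block pairs.
- **Sections 3.3 and 7.2.** Their silence is not particular to ON-TOP. Section 3.3 names no treatment-phase outcome, and the general model wording in 7.2 would cover ON-TOP if it were collected. The decisive gap is in scheduling.
- **Reach.** This is one of five secondary objectives, and no power or error-rate figure depends on it.

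**Conclusion.** The concern holds. Following the plan as written gives one ON-TOP value per patient, before any dose, and none on LDX or placebo. Objective 5 cannot be answered. The 0 of 86 and 0 of 40 counts rest on the single Visit 2 mark in the table, the absence of ON-TOP from the visit text, and the retention figures in Section 3.1. They count completers only and assume no effect size or correlation. The primary comparison is unaffected, so this is a correction that should be made rather than a threat to the trial's main result.

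**What to change.** Either make ON-TOP a measured treatment outcome or drop the objective.

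**To keep it:**

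- Retain the Visit 2 value and name it in Section 6.2.
- Add ON-TOP at Visits 6, 7 and 11 in the table and in Sections 6.4, 6.6 and 6.8. Visits 6 and 11 give the treatment contrast. Visit 7 gives the block 2 baseline, as the visit text already does for BRIEF-A and BFIS.
- State in Section 7.2 that ON-TOP is a treatment-phase outcome and which score is analysed.

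The cost is about 46 + 44 + 40 = 130 administrations of one rating scale at existing visits, plus one more secondary outcome to report.

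**To drop it:** delete Objective 5.

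**Separately,** check the source table against Sections 6.1 to 6.9. This is clerical work, and some or all of the differences may come from the PDF conversion.

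- CANTAB, WAIS, BRIEF-A and BFIS differ from the visit text as tabulated above. The end-of-block-1 assessments in Section 6.4 should appear at Visit 6. Sections 3.1, 4.3 and 7.1 also place BRIEF-A and a functional impairment measure in the screening evaluation.
- ADHD-RS, the Barkley SCT Scale and CGI are blank at Visit 3 in the table but required there by Section 6.3.
- C-SSRS is marked at Visits 2, 3, 7, 8 and 11, while the text has Visits 1, 2 and 11.
- Dispensing is marked at Visits 3–6 and 9–11, while the visit text has Visits 2–10 and Section 5.2 says none before week 1.

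The C-SSRS and dispensing passages must be reconciled; no view is taken here on which is right.

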### 3 Study Design

#### 3.1 General Design

- 1) Total number of subjects/Total sample size: Approximately 120 patients with ADHD (with the final number of subjects depending on the proportion of ADHD subjects who have SCT; we have based our projections on an estimated 50% prevalence) in the phenotype phase (screening visit); 50 adults with ADHD and SCT+ will enter the treatment phase with LDX and placebo. We will analyze data from all subjects who take at least one dose of medication in both blocks. Using a 20% drop-out rate to occur throughout the trial, we estimate that approximately 50 subjects will enroll in the trial; 46 patients will complete the first phase of treatment, 44 patients will complete the intervening placebo washout, and 40 patients will complete each treatment phase.
- 2) Justification for sample size: We will enroll a sufficient number of subjects to recruit 80 patients with ADHD and SCT to enter the treatment study. The 50% prevalence of SCT in adult ADHD has been established in community samples [1, 2]. Power for this study was calculated using PASS [22] based on the primary outcome, i.e. change between baseline and week 4 of treatment on the Barkley SCT scale. Previous studies suggest that the upper bound of the effect size for the comparison of ADHD

CONFIDENTIAL

medications vs. placebo for ADHD symptoms varies between 1.2 and 1.5 standard deviations. Using a conservative estimate of effect that is half as robust for SCT as ADHD we based on our calculations on a 0.6 ES for SCT symptoms. The primary comparison will be a reduction in SCT symptoms on LDX vs. placebo. With 45 evaluable patients with SCT we will have 80% power to detect an effect size (ES) of 0.6 using a two-sided test with a type I error of 0.05.

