### 7.3 Subject Population(s) for Analysis

All subjects will be entered into the analysis including:

All-randomized population: Any subject randomized into the study, regardless of whether they received study drug

All-treated population: Any subject randomized into the study that received at least one dose of study drug

Protocol-compliant population: Any subject who was randomized and received the protocol required study drug exposure and required protocol processing

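### Section 3.1 analyses only patients dosed in both blocks, which conflicts with the intention-to-treat primary analysis in 7.2 and the populations in 7.3; on the plan's own attrition it excludes at least 6 of about 50 patients (12%).

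*Combined protocol and SAP*

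**What the plan says.** Section 3.1, item 1, on the total sample size, says: "We will analyze data from all subjects who take at least one dose of medication in both blocks". It then projects attrition: "Using a 20% drop-out rate to occur throughout the trial", about 50 enrol, "46 patients will complete the first phase of treatment, 44 patients will complete the intervening placebo washout", and 40 complete each treatment phase.

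Section 7.2 starts its population statement with "Our primary analyses will be intention" to treat, and adds that "we will explore the data with less conservative per protocol analyses". On missing data it says: "Because this is a randomized trial, which follows subjects over a short period of time, missing data is not expected to impact our analyses". The next sentence gives imputation in Stata as a fallback if missing data does become a problem.

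Section 7.3 opens with "All subjects will be entered into the analysis including" and lists three populations. The all-randomised set is "Any subject randomized into the study, regardless of whether they received study drug". The all-treated set needs one dose of study drug and does not mention blocks. The third is a protocol-compliant set. None is labelled primary.

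Section 5.2 describes Block One, the placebo washout and Block Two separately, so a washout capsule is not a block-2 dose.

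**The concern.** Taking a first block-2 dose happens at least six weeks after the first treatment is assigned. A rule that depends on it is not intention to treat, and it matches none of the sets in 7.3. An analyst could follow either section and claim to have kept to the plan, and that choice could be made after the data are seen.

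Two things are at stake. Observed block-1 ratings would be discarded, although the 7.2 model (treatment, visit, order and their interactions) can use patients with one block only. The treatment estimate could also be biased, but only if loss before block 2 is related to outcome and either the number or the mechanism of losses differs between the orders.

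The plan gives reasons why mechanisms might differ in block 1. Discontinuation for the listed drug side effects (section 1.6.1) bears more on patients who start on LDX. Withdrawal for a 30% decline, or for lack of efficacy (sections 8.4 and 8.5), may bear more on those who start on placebo. In the washout both orders take placebo (section 5.2), so the argument covers those losses less directly.

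**Working it through.** **1. The plan's attrition.** 50 × (1 − 0.20) = 40. Stage by stage: 50 − 46 = 4 lost in block 1, 46 − 44 = 2 in washout, 44 − 40 = 4 in block 2; 4 + 2 + 4 = 10 = 20% of 50. The projection is coherent. (Item 2 of section 3.1 also mentions 80 patients entering the treatment study. That is a separate conflict and is not used here.)

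**2. Who can meet the rule.** Nobody who leaves before the end of washout can take a block-2 dose, so the ceiling is 44. Excluded: at least 50 − 44 = 6, and 6/50 = 12%. It is at least 6 because some who finish washout may take no block-2 dose.

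**3. Ratings discarded.** The two washout losses have completed block 1. The section 6 schedule marks post-baseline Barkley SCT ratings at Visits 4, 5 and 6, so 2 × 3 = 6 ratings are lost, two of them week-4 scores. If Visit 3 is also rated, as section 6.3 says, it is 2 × 4 = 8. The four block-1 losses would add whatever they had before leaving.

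**4. Power.** Section 3.1 counts 45 evaluable patients for 80% power at 0.6 SD. Two readings come close: 45 per group gives 80.4% (two-sample t), and 45 pairs with zero within-patient correlation gives 79.5%. At 44 they give 79.5% and 78.6%, about one point less. Power is not the issue.

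**5. Possible bias (illustration).** Assumptions, not from the documents: 25:25 by order (section 5.3 gives no ratio); correlations 0.5 between and 0.7 within blocks; effect rising linearly to 0.60 SD at week 4; four losses after week 2, two in washout and four in block 2 (two per order). Outcome-driven means that the patient with the worst latest score leaves. The model is generalised least squares with known covariance, with period-by-week and treatment-by-week terms and both baselines as responses. The true value is 0.60, and the SD of the estimate is about 0.14. Where two values are shown, the first has more, or the only, outcome-driven loss in the LDX-first order and the second in the placebo-first order.

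| Loss before block 2 | Both-blocks estimate |
|---|---|
| 6:0, all outcome-driven | 0.657 / 0.545 |
| 6:0, about half outcome-driven | 0.632 / 0.570 |
| 4:2, outcome-driven | 0.610 / 0.592 |
| 3:3, outcome-driven in one order only | 0.632 / 0.571 |
| 3:3, same mechanism | 0.599 |
| 6:0, random | 0.603 |

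The first row is a shift of 0.057/0.14 = 0.41 SD. Other assumptions go further. Without baselines, 6:0 gives 0.673 with SD about 0.15, so 0.073/0.15 = 0.49 SD. With correlations 0.3 and 0.6 it gives 0.680 with SD about 0.164, so 0.080/0.164 = 0.49 SD. If the two washout losses are random, 6:0 falls to 0.613 / 0.583.

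If loss is unrelated to order, the number of the six from one order is hypergeometric (6 drawn from 25 + 25): 6:0 2%, 5:1 17%, 4:2 48%, 3:3 33%. So 48% + 33% = 81% of trials split 4:2 or 3:3.

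**6. All randomised patients instead.** The same likelihood-type model gives 0.598 to 0.604 throughout. Section 7.2 names GEE, where the result depends on the working correlation (point estimates, all randomised versus both-blocks):

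- Exchangeable, 6:0: 0.637 / 0.568 versus 0.672 / 0.532.
- Exchangeable, 3:3 one order: 0.602 / 0.595 versus 0.619 / 0.578.
- Independence, 6:0: 0.610 / 0.594 versus 0.685 / 0.519.
- Independence, 3:3 one order: 0.550 / 0.644 versus 0.588 / 0.606. Here the larger set is further from 0.60.

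**The case against.** The best defence is that section 7 is the statistical plan. Intention to treat in 7.2 together with an all-randomised set in 7.3 shows the intent, while the 3.1 sentence sits among recruitment projections and does not call its rule primary. That lowers the weight of the point but does not remove it. The sentence states without qualification whose data will be analysed, section 7 does not say that it overrides 3.1, and 7.3 names no primary set.

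The phrase about both blocks could also be attached to the data rather than to the dosing: data from both blocks, for anyone who took a dose. That would match the all-treated set, but it is a strained reading of the word order.

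The numerical objections largely stand. The bias is small or absent in most scenarios, and its direction is unknown. The value near 0.60 for all randomised patients is built into the set-up: the score that drives loss is observed, so data are missing at random, and the covariance is known. Under an independence GEE the larger set can be the worse one.

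On missing data, 7.2 expects no impact rather than no drop-out, and it does offer imputation. The sentence is optimistic beside a planned 20% drop-out, but this is secondary.

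**Conclusion.** The plan is wrong as written: two incompatible rules say whose data are analysed, and nothing reconciles them. The firm figure is the exclusion of at least 6 of about 50 patients (12%), two of them with a completed block 1. It rests only on the plan's own projection and on treating those who enrol in the treatment phase as randomised.

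The bias is a possibility, not a finding. Under the stated assumptions it runs from none to roughly half of the estimate's SD in extreme cases, and is usually much smaller.

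A reader might infer three stronger things that the documents do not support:

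- That the plan commits to a both-blocks primary analysis. Section 3.1 never calls its rule primary, and 7.2 says intention to treat.
- That the drug effect will be biased in a known direction. The documents give neither the outcome-driven share of losses nor their split by order. Unequal numbers alone do not cause bias, and equal numbers do not exclude it.
- That analysing everyone removes the bias. That needs missing at random and a suitable model.

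This should be fixed, preferably before unblinding, on grounds of consistency and of closing off a choice of population after the fact.

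**What to change.** 1. In 3.1, delete the both-blocks sentence or label it a sensitivity set.
2. In 7.3, name all randomised patients as the primary population for the 7.2 intention-to-treat analysis, with every available rating from either block used, so that patients with block-1 data only contribute.
3. In 7.2, state a likelihood-based mixed model or a non-independence GEE working correlation, because the benefit against bias depends on it.
4. Secondary: reword the missing-data sentence in 7.2 to fit the planned 20% drop-out, keeping the imputation fallback and saying how it would be done.

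The cost is wording in three sections, with no new visits or data and no change to any withdrawal or dosing rule. The downside is that the all-randomised analysis relies on missing at random, and with an independence GEE it is not always closer to the truth. A missing-not-at-random sensitivity analysis would be a useful optional addition.
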